## 7.1. Treatments Administered

Study Treatment Name:	Bisphosphocin®	Placebo		
Dosage formulation:	Gel	Gel		
Unit dose strength(s)/Dosage level(s):	5% or 10% concentration	Not applicable		
Route of Administration	Topical administration	Topical administration		
Dosing instructions:	Gel to be applied twice daily (BID) for 28 days	Gel to be applied twice daily (BID) for 28 days		
Packaging and Labeling	Test Product kits will be labelled and contain 18 applicators individually packaged in a foil pouch. These kits will be prelabelled with Batch/Expiration Dating/study and kit ID numbers. used for dose administration.	Matching placebo kits will be labelled and contain 18 applicators individually packaged in a foil pouch. These kits will be pre-labelled with Batch/Expiration Dating/study and kit ID numbers. used for dose administration.		

## 7.2. Standard of Care

Currently accepted cDFU SOC involves four principles:

- 1. Pressure relief or off-loading
- 2. Proper ulcer cleaning and debridement procedures with post procedure irrigation with normal saline
- 3. Infection management as defined by Lipsky et al, 2012 Infection Guidelines
- 4. Revascularization when indicated.

During the SOC Run-in phase, a commercially available hydrogel will be used to keep the wound moist, whereas either Nu-3 gel, or placebo gel will be used during the treatment arm. Mepitel or equivalent will be trimmed to cover the entire dimension of the ulcer and overlaid into the ulcer. This will then be covered by Tegaderm. Padding and Coban Lite 2- layer dressing or equivalent will be placed over the Mepitel or equivalent.

## 7.3. Dose Escalation

The decision to proceed to the next dose level of Nu-3 Gel will be made by the DMC based on safety and tolerability data obtained in each cohort. Review of the data will occur concurrent with the 14-day safety follow-up period.

This decision will be based on pre-defined DLT, which will be detailed in the DMC Charter. The MTD will be considered as the dose level below that for which a DLT was observed. If the criteria for a DLT occurs in the initial dosing cohort then the study will be halted.

Details regarding responsibilities of the DMC are outlined in a separate charter.

# 7.4. Method of Treatment Assignment

All subjects will be centrally assigned to randomized study treatment using an automated system. Before the study is initiated, directions for use will be provided to each site.

Returned study treatment should not be re-dispensed to the subjects.

# 7.5. Blinding

The contents of the study treatment kits will not be known to the pharmacist, designee, clinical staff, the CRO or Sponsor. Upon randomization of the subject, the pharmacist or designee will receive a randomization number and an associated Test Product Kit number of a kit at the site. The matching kit will then be dispensed to the subject for dose administration on the first week of the study. On subsequent visits the pharmacist or designee will receive additional Test Product Kit numbers that will match the Test Product Kits that have been delivered to the site.

The IVRS/IWRS will be programmed with blind-breaking instructions. The blind may be broken if, in the opinion of the investigator, it is in the subject's best interest for the investigator to know the study treatment assignment. The sponsor must be notified before the blind is broken unless identification of the study treatment is required for a medical emergency in which the knowledge of the specific blinded study treatment will affect the immediate management of the subject's condition. In this case, the sponsor must be notified within 24 hours after breaking the blind. The date and reason that the blind was broken must be recorded in the source documentation and CRF, as applicable.

# 7.6. Preparation/Handling/Storage/Accountability

The investigator or designee must confirm appropriate temperature conditions have been maintained during transit for all study treatment received and any discrepancies are reported and resolved before use of the study treatment.

Only subjects enrolled in the study and their caregivers may receive and apply the study treatment and only authorized site staff may supply the study treatment. While at the clinical site, all study treatments should be stored in a secure, environmentally controlled, and monitored (manual or automated) area in

accordance with the labeled storage conditions (2-8 °C) with access limited to the investigator and authorized site staff. Subject and caregivers will be instructed to keep the product refrigerated while stored at their home.

The investigator, institution, or the head of the medical institution (where applicable) is responsible for study treatment accountability, reconciliation, and record maintenance (i.e.., receipt, reconciliation, and final disposition of records).

Study treatment will be dispensed as Product Test Kits at the study visits as summarized in the Schedule of Events.

Subjects will be instructed to bring empty and unused drug applicators back to the site at V4, V5, V6 and V7. Returned study drug should be handled according to the drug accountability guidelines provided and under no circumstances can returned Product Test Kits or their contents be re-dispensed to the subjects.

Treatment compliance will be assessed by the dispensing and return records in the subject's case report form (CRF).

# 7.7. Concomitant Therapy

Any medication or vaccine (including over the counter or prescription medicines, vitamins, and/or herbal supplements) that the subject is receiving for 30 days prior to screening for the trial or receives during the study must be recorded along with:

- Reason for use
- Dates of administration including start and end dates
- Dosage information including dose, route and frequency

The Medical Monitor should be contacted if there are any questions regarding concomitant or prior therapy.

#### 7.7.1. Prohibited Medications

Immunosuppressive agents including systemic corticosteroids, are prohibited. Inhaled or topical steroids are allowed.

Wound care products such as Regranex® (rhPDGF), Apligraft®, Dermagraft®, Oasis®, as well as any other skin equivalents or topical growth factors, are excluded for use during this trial. Wound cleansers containing antiseptics are prohibited for use during this study. Hyperbaric oxygen (HBO) treatment is also excluded. The use of silver nitrate sticks, styptic pencils or electrocautery is prohibited.

# 8. CLINICAL PROCEDURES

Subjects will have the study explained to them and will be provided the study specific informed consent form (ICF). The screening evaluations will be performed after the subject has been given the opportunity to ask questions and has signed a written informed consent. For subjects enrolled in the study, activities will consist of two screening/ SOC Run-in visits and six scheduled visits (total = 8 visits). Screening will begin at Day -14, 7 days (± 2 days) prior to the beginning of the Run-In visit, Day -7, 7 days before baseline.

#### General Information Visits 3-7:

Eligible subject's caregivers will apply Test Product twice daily, approximately 12 hours apart and at approximately the same times each day. Test Product will be applied topically to the target ulcer from a single dose applicator. The target ulcer will be dressed with Mepitel or equivalent which will be trimmed to cover the entire dimension of the ulcer and overlaid into the ulcer, followed by Tegaderm dressing covering the entire dimension of the ulcer. Padding and Coban Lite 2- layer dressing or equivalent will be placed over the Mepitel, or equivalent, covered with Tegaderm.

The subject and caregiver will be instructed to leave the bandage on the wound until applying the next dose and thereafter morning and evening for 28 days. Subjects and caregivers will be given written instructions on the proper care and hygiene to include keeping the ulcer clean and bandage dry at V3. The subject WILL NOT apply gel or change dressing on the day of their final visit.

Standardized offloading will continue over the course of the study. For all visits during the treatment period, if subjects are seen at the clinic before mid-day, the caregiver will not replace the dressing applied the evening before prior to the clinic visit, until after the visit procedures are complete. The caregiver will then apply the morning dressing.

If subjects are seen at the clinic after mid-day, they will replace the gel dressing in the morning. After all the visit procedures are complete the caregiver will apply in the clinic the evening dressing and leave in place until the following morning.

#### Visit 1 (Day -14 prior to baseline (+/- 2 days)) Screening:

- Informed consent and confirmation of eligibility
- Baseline subject disease assessments (as specified in the Schedule of Events table)
- Collect Demographic Data
- Twelve-month medical history
- Targeted physical examination: Perform a physical exam.
- Vital signs measurements: Weight, temperature, resting blood pressure, heart rate, and respiratory rate. Vital signs are to be obtained prior to collecting laboratory samples.
- Safety Laboratory Tests including tests noted in section 11.5.4
- For females of child-bearing potential: the pregnancy test (serum) performed at screening
- Selection of the target ulcer
- Screening Ulcer Assessment: Visual examination of selected target ulcer before and after debridement.
- The target ulcer is classified according to the Wagner Scale.

- Two wound swabs, one for culture and one for microflora examination will be taken BEFORE debridement or any cleansing. Samples collected in accordance with the Microbiological Assessment Appendix 5
- Sharp excisional debridement in accordance with debridement section of the Standard of Care Appendix 4
- Digital photos taken before and after debridement by site staff. Two photos are to be taken from a focal distance of 18 inches, and one photo taken close-up for a total of three digital images
- Employ an advanced digital imaging system to accurately measure the target foot ulcer dimensions following debridement
- Measure Transcutaneous oxygen pressures (TcPO2), obtain Ankle brachial pressure index or biphasic/triphasic doppler ultrasound
- Subject and care giver trained in application of dressing in accordance with the Appendix 4
- Hydrogel and SOC dressing applied in accordance with the Standard of Care Appendix 4
- Review and dispense subject instruction sheet
- Record all adverse events (local and systemic), concurrent procedures, and changes in concomitant medications on the source documents and case report forms (eCRFs)
- Dispense offloading RCW accordance with Appendix 6 and review expectations
- Begin offloading in accordance with Appendix 6

Visit 2 (Day -7 (+/- 2 days)) Run-In: All subjects will return to the clinic to be seen for wound care and ulcer examination. The following assessments will be completed at this visit.

- Vital signs measurements: Weight, temperature, resting blood pressure, heart rate, and respiratory rate
- Run-in Ulcer Assessment: Visual examination of chronic ulcer before and after debridement
- Sharp excisional debridement is allowed if necessary at Investigator's discretion
- Pre and post debridement digital photos taken by site personnel, if debridement is required. Two
  photos are to be taken from a focal distance of 18 inches, and one photo taken close-up for a total
  of three digital images
- Employ an advanced digital imaging system to accurately measure the target foot ulcer dimensions following debridement
- Evaluate wound healing and discontinue any subject with a  $\ge 30\%$  or greater reduction in area as shown by the advanced digital imaging measurements
- Continued offloading applied in accordance with Appendix 6
- Hydrogel and SOC dressing applied in accordance with the Appendix 4

Visit 3 (Day 0) Baseline: All subjects will return after the screening period for assessment of study participation criteria and if these are satisfied, the subjects will be randomly assigned to Nu-3 gel or placebo gel treatment. Subject disease assessments will be performed as specified in the schedule of events table.

- Vital signs measurements: Weight, temperature, resting blood pressure, heart rate, and respiratory rate. Vital signs are to be obtained prior to collecting laboratory samples
- Urine pregnancy test for WOCBP prior to randomization.
- Serum pregnancy test will also be conducted for WOCBP

- 12 Lead ECG
- Safety Laboratory tests
- Baseline Ulcer Assessment: Visual examination of chronic ulcer before and after debridement (if required, only LIGHT debridement is allowed)
- Two wound swabs, one for culture and one for microflora examination are taken BEFORE debridement
- Light debridement, only if required
- Digital photos should be taken pre and post debridement, if debridement is required. Two photos
  are to be taken from a focal distance of 18 inches, and one photo taken close-up for a total of three
  digital images
- Employ an advanced digital imaging system to accurately measure the target foot ulcer dimensions following debridement
- Subject randomized within electronic RTSM, obtaining kit number
- Subjects will be provided with his/her first designated test product kit and instructed to apply the product twice daily for 1 weeks (7±2 days). Test product application will be demonstrated, and subject instruction sheet reviewed, using the assigned test product
- The caregiver will be observed applying the first dose in the clinic to ensure compliance administering Test Product topically to the diabetic foot ulcer and surrounding intact skin. The target ulcer will be dressed with Mepitel, or equivalent, which will be trimmed to cover the entire dimension of the ulcer and overlaid into the ulcer, followed by Tegaderm dressing covering the entire dimension of the ulcer. Padding and Coban Lite 2- layer dressing or equivalent will be placed over the Mepitel, or equivalent, covered with Tegaderm
- The subject will be scheduled for the next study visit, with a reminder to bring the test article kit, including all tubes, whether they are empty, partially empty and/or unused tubes to the visit
- Record all adverse events (local and systemic), concurrent procedures, and changes in concomitant medications during the study on the source documents and case report forms (eCRFs)
- Continue offloading applied in accordance with Appendix 6

Visit 4 (Day 7±2 days.): Subjects will return after applying test product for 7 (+/- 2) days every 12 hours. Subject disease assessments will be performed as specified in the schedule of events table.

- Vital signs measurements: Weight, temperature, resting blood pressure, heart rate, and respiratory
- Ulcer Assessment: Visual examination of chronic ulcer before and after light debridement (if necessary)
- Light debridement, only if required
- Digital images should be taken pre and post debridement with the sponsor provided digital camera, if debridement is required. Two photos are to be taken from a focal distance of 18 inches, and one photo taken close-up for a total of three digital images
- Employ an advanced digital imaging system to accurately measure the target foot ulcer dimensions following debridement (if debridement is required)
- Collect Test Product kit dispensed on Day 0, determine accountability
- Subjects will be provided with his/her second designated test product kit and instructed to apply the product twice daily for 1 week (7±2 days)

- Two wound swabs, one for culture and one for microflora examination are taken BEFORE debridement, if the wound is still open
- The subject will be scheduled for the next study visit, with a reminder to bring the test article kit and tubes, including empty, partially used, and unused tubes to the visit
- Record all adverse events (local and systemic), concurrent procedures, and changes in concomitant medications during the study on the source documents and case report forms (eCRFs)
- Continue offloading applied in accordance with Appendix 6

Visit 5 (Day 14±2 days): Subjects will return after applying test product for another 7 (+/- 2) days every 12 hours. Subject disease assessments will be performed as specified in the schedule of events table.

- Vital signs measurements: Weight, temperature, resting blood pressure, heart rate, and respiratory rate. Vital signs are to be obtained prior to collecting laboratory samples
- Safety Laboratory tests
- Serum pregnancy
- Ulcer Assessment: Visual examination of target ulcer before and after light debridement (only if required by Investigator.)
- Light debridement, only if required
- Take digital photos with sponsor provided camera both pre and post debridement, if debridement is required. Two photos are to be taken from a focal distance of 18 inches, and one photo taken close-up for a total of three digital images
- Employ an advanced digital imaging system to accurately measure the target foot ulcer dimensions following debridement, if performed
- Two wound swabs, one for culture and one for microflora examination are taken BEFORE debridement, if the wound is still open
- Collect kit dispensed on Day 7, determine accountability
- Subjects will be provided with his/her third designated test product kit and instructed to apply the product twice daily for 1 week (7±2 days)
- The subject will be scheduled for the next study visit, with a reminder to bring the test article kit
  and tubes including empty, partially used and unused tubes to the visit
- Record all adverse events (local and systemic), concurrent procedures, and changes in concomitant medications during the study on the source documents and case report forms (eCRFs)
- Continue offloading applied in accordance with Appendix 6

Visit 6 (Day 21±2 days.): Subjects will return after applying test product for 7 (+/- 2) days every 12 hours. Subject disease assessments will be performed as specified in the schedule of events table.

- Vital signs measurements: Weight, temperature, resting blood pressure, heart rate, and respiratory rate
- Ulcer Assessment: Visual examination of chronic ulcer before and after debridement (only if required by Investigator).
- Light debridement, only if required
- Take digital images with sponsor provided camera both pre and post debridement, if debridement is required. Two photos are to be taken from a focal distance of 18 inches, and one photo taken

- close-up for a total of three digital images
- Employ an advanced digital imaging system to accurately measure the target foot ulcer dimensions following debridement (if debridement is performed, only light debridement may be performed).
- Two wound swabs, one for culture and one for microflora examination are taken BEFORE debridement, if the wound is still open
- Collect kit dispensed on Day 14, determine accountability
- Subjects will be provided with his/her fourth and final designated test product kit and instructed to apply the product twice daily for 1 week (7±2 days).
- The subject will be scheduled for the next study visit, with a reminder to bring the test article kit and all tubes including empty, partially used and unused tubes to the visit.
- Record all adverse events (local and systemic), concurrent procedures, and changes in concomitant medications during the study on the source documents and case report forms (eCRFs).
- Continue offloading applied in accordance with Appendix 6

Visit 7 (Day 28±2 days): The study subject will return for final efficacy evaluation to the clinical site on Day 28±2 days. At that visit, the subject will undergo the following procedures and evaluations.

- Vital signs measurements: Weight, temperature, resting blood pressure, heart rate, and respiratory rate. Vital signs are to be obtained prior to collecting laboratory samples
- 12 Lead ECG
- Safety Laboratory Tests
- Serum pregnancy
- Ulcer Assessment: Visual examination of chronic ulcer.
- No debridement to be performed at this visit
- Two wound swabs will be taken, one for microbiological culture and one for microflora examination (unless ulcer has completely re-epithelialized).
- Take digital photos with the digital camera provided by sponsor. Two photos are to be taken from a focal distance of 18 inches, and one photo taken close-up for a total of three digital images
- Employ an advanced digital imaging system to accurately measure the target foot ulcer dimensions.
- Collect kit dispensed on Day 21, perform drug accountability
- Record all adverse events (local and systemic), concurrent procedures, and changes in concomitant medications during the study on the source documents and case report forms (eCRFs).
- Continue offloading applied in accordance with Appendix 6

If the ulcer remains open at visit 7, subjects will be given a supply of non-abrasive bandages and written instructions on weekly ulcer care until the Day 42 follow up visit (Visit 8). In addition, subjects will be told to call if there is any worsening of the ulcer with regard to pain, signs of infection, or swelling.

Standardized offloading will continue until the final study visit (Day 42±2 days) regardless of wound healing status.

Visit 8 (Day 42±2) End of Study (EOS) Visit: The subject shall attend final end-of-study 42±2 days post

Randomization. At this follow-up visit, the subject will undergo the following procedures and evaluations.

- Vital signs measurements including weight, temperature, resting blood pressure, heart rate, and respiratory rate. Vital signs are to be obtained prior to collecting laboratory samples
- 12 Lead ECG
- Physical examination
- Safety Laboratory Tests
- For females of child-bearing potential: pregnancy test (serum) to be performed
- Ulcer Assessment: Visual examination of chronic ulcer.
- Take digital photos with the digital camera provided by sponsor. Two photos are to be taken from a focal distance of 18 inches, and one photo taken close-up for a total of three digital images
- Employ an advanced digital imaging system to accurately measure the target foot ulcer dimensions
- Record all adverse events (local and systemic), concurrent procedures, and changes in concomitant medications during the study on the source documents and case report forms (eCRFs)
- Physician may perform or not perform debridement according to his practice standards
- Offloading ends

Early Termination Visit: If a subject withdraws prior to completing the study, the reason for withdrawal will be documented. If a subject withdraws early due to a Serious Adverse Event, he/she will be followed until resolution/stabilization of the SAE.

If a subject prematurely withdraws from the study, subject will be asked to complete the study procedures and evaluations performed in the final study visit at the time of withdrawal from the study:

- Vital signs measurements including weight, temperature, resting blood pressure, heart rate, and respiratory rate. Vital signs are to be obtained prior to collecting laboratory samples
- 12 Lead ECG
- Physical examination
- Safety Laboratory Tests
- For females of child-bearing potential: serum pregnancy test to be performed.
- Ulcer Assessment: Visual examination of chronic ulcer
- No debridement to be performed at this visit
- Two wound swabs will be taken, one for microbiological culture and one for microflora examination (unless ulcer has completely re-epithelialized)
- Take digital photos with the digital camera provided by sponsor. Two photos are to be taken from a focal distance of 18 inches, and one photo taken close-up for a total of three digital images
- Employ an advanced digital imaging system to accurately measure the target foot ulcer dimensions.
- Offloading ends
- If early termination occurs before Day 28 the following should be completed:
  - o Two wound swabs, one for culture and one for microflora examination, are collected, if the wound is still open
  - o Collect kit dispensed on prior study visit, if applicable and determine accountability

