# 9. SCHEDULE OF EVENTS

	Scree	Screening		Treatment		EOS	Early Termination		
	Visit 1 Screening	Visit 2	Visit 3 Baseline	Visit 4	Visit 5	Visit 6	Visit 7 Final	Visit 8 Follow-up	ET
Event	-14 Day (±2 days)	-7 Day (±2 days)	Day 0 (±2 days)	Day 7 (±2 days)	Day 14 (±2 days)	Day 21 (±2 days)	Day 28 (±2 days)	Day 42 (±2 days)	
Eligibility Screening, Inclusion, Exclusion Criteria	Х		Х						
Informed Consent	Х								
Demographics & Medical History	Х								
Physical Exam	Х							Х	Х
Vital Signs	Х	Х	Х	Х	Х	Х	Х	Х	Х
Transcutaneous oxygen pressures, ABI's, doppler ultrasound and Ischemic Index	Х								
12 Lead ECG			Х				Х	Х	Х
Urine Pregnancy Test (2WOCBP)			Х						
Serum Pregnancy Test (  WOCBP)	Х		х		Х		х	Х	Х
Laboratory Tests – Safety Labs	X 		Х		Х		Х	Х	Х
Concomitant Medication and Adverse Event Review	X								
Visual Examination of Chronic Ulcer	Х	Х	Х	Х	Х	Х	х	Х	Х
Wound Culture Swab Pre- Debridement	Х		Х	X 6	X 	X 	X 6		X 
Microflora Swab Pre - Debridement	Х		Х	X 	X 	X 	X 		X 
Advanced digital imaging system Post -Debridement	х	х	Х	х	Х	Х	X 	Х	X 
Digital images before and after debridement (sponsor provided camera)	х	х	Х	х	х	х	X 	х	X 
Offloading	х	х	х	х	х	х	х	Study Off- Loading Ends	Study Off- Loading Ends
Subject Instruction Sheet Reviewed & Distributed	Х		х						
Randomization within RTSM			Х						
Dispense Test Article			Х	х	Х	Х			
Assess Subject Compliance Test Article Accountability				х	х	Х	Х		X 

ı	Debridement 1	SD-R	SD-P	LSD	LSD	LSD	LSD	None	SD-P	None
ı									il '	1 '

Sharp excisional debridement is required at V1 (SD-R), permissible (SD-P) at V2 and prohibited at subsequent visits. Only light debridement (LSD) is allowed at subsequent visits at the Investigator's discretion per appendix.

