Women of childbearing potential (WOCBP) include any female who has experienced menarche and who has not undergone successful surgical sterilization (hysterectomy, bilateral tubal ligation, or bilateral oophorectomy) or is not postmenopausal [defined as amenorrhea >12 consecutive months]. Even women who are using oral, implanted, or injectable contraceptive hormones, an intrauterine device (IUD), barrier methods (diaphragm, condoms, spermicidal) to prevent pregnancy, practicing abstinence, or where partner is sterile (e.g., vasectomy performed at least six months prior to the subject's initiation of treatment) should be considered to be of childbearing potential.

At Visit 7 no debridement occurs but all imaging will still be captured

Only performed if early termination occurs prior to Visit 7

HbA1c collected

Swabs will not be performed if the wound is closed

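### The Visit 4 and 5 area-imaging lines, and the Visit 4 to 6 photo lines, can be read as applying only when debridement is done, although the Schedule of Events marks both at every visit

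*Protocol*

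**What the plan says.** **Visit text (Protocol Section 8).** At Visits 4, 5 and 6 light debridement is done only where it is needed. The imaging lines differ by visit:

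- Visit 4, area: measured "following debridement (if debridement is required".
- Visit 5, area: "measure the target foot ulcer dimensions following debridement, if performed".
- Visit 6, area: measured following debridement, with a parenthesis that reads "if debridement is performed, only light debridement may be performed". This limits the type of debridement and does not clearly make the measurement conditional.
- Photos at Visits 4 to 6: conditional at all three. Visit 6 reads "Take digital images with sponsor provided camera both pre and post debridement, if debridement is required".
- Visits 2 and 3, where debridement is also optional: the area line has no condition. The photo line does.
- Visits 7 and 8: area and photos are unconditional.

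**Schedule of Events (Protocol Section 9).** The row "Advanced digital imaging system Post -Debridement" and the photo row are marked at every visit. Footnote 3 is attached to Visit 7 and early termination only, and reads "At Visit 7 no debridement occurs but all imaging will still be captured".

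**SAP.** Missing continuous outcomes are imputed by LOCF (Missing data). PAR is calculated against the area at randomization and is reported by week and treatment group in a table and a plot (Analysis, efficacy items).

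**The concern.** Two parts of the protocol give different answers to a practical question: is an ulcer that needs no debridement at Visit 4 or 5 measured that day? The Schedule says yes. The visit text can be read as no. The area line is unconditional at Visits 2 and 3 and gains its condition at Visits 4 and 5, so a coordinator could take the change as intended. The one sentence confirming that imaging goes ahead without debridement names Visit 7 only.

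Any resulting gap would probably not be random. Appendix 4 describes debridement as removal of non-viable and necrotic tissue, so an ulcer spared it is likely to be cleaner, or closed. That is an inference; the documents do not state it. If it is right, missingness depends on the quantity being measured, and LOCF replaces an improving ulcer's area with an older one. A closed ulcer is the extreme case, because the SAP has no rule that sets the area of a healed ulcer to zero.

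Ulcer surface area is a named secondary variable, each active group has only 12 subjects, and an image not taken cannot be recovered later. A missed photo would simply be absent; the SAP plans no numerical analysis of photos.

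**Working it through.** The plan gives no figure to reproduce. The check compares the texts and then illustrates the LOCF effect.

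**Step 1: which area points are exposed**

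| Visit | Debridement | Area line in visit text | Schedule |
|---|---|---|---|
| 2, 3 | optional | no condition | marked |
| 4 (Day 7) | optional, light | conditional wording | marked, no condition |
| 5 (Day 14) | optional, light | conditional wording | marked, no condition |
| 6 (Day 21) | optional, light | limits the type of debridement only | marked, no condition |
| 7 (Day 28) | none | unconditional | marked, footnote 3 |
| 8 (Day 42) | optional | unconditional | marked |

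Two of the four on-treatment area points are exposed: Days 7 and 14. Photos are exposed at Visits 4, 5 and 6.

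**Step 2: effect on one ulcer**

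Inputs: the SAP formula PAR = ((A1 − A2)/A1) × 100, with A1 the area at randomization, and the SAP LOCF rule. The documents give no shrinkage rate, so a constant weekly rate *r* is assumed, with a range of 5% to 20%. Then A2 after *w* weeks is A1 × (1 − r)^w, and true PAR = 100 × (1 − (1 − r)^w). It is also assumed that LOCF may carry the baseline value, which the SAP does not rule out.

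| Assumed *r* | True PAR, Days 7/14/21/28 | PAR if not imaged at Visits 4 and 5 |
|---|---|---|
| 5% | 5.0 / 9.8 / 14.3 / 18.5 | 0 / 0 / 14.3 / 18.5 |
| 10% | 10.0 / 19.0 / 27.1 / 34.4 | 0 / 0 / 27.1 / 34.4 |
| 20% | 20.0 / 36.0 / 48.8 / 59.0 | 0 / 0 / 48.8 / 59.0 |

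Worked line, r = 10%, Day 14: 100 × (1 − 0.9²) = 100 × (1 − 0.81) = 19.0. With the baseline area carried forward, A2 = A1 and PAR = 0. If Visit 4 is imaged and only Visit 5 is skipped, Day 14 reads 10.0, an error of 19.0 − 10.0 = 9.0 points.

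**Step 3: effect on a group mean at Day 14**

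Let a share *f* of the group be not imaged at Visits 4 and 5 (assumed 25%, 50% or 75%; in a group of 12 that is 3, 6 or 9 subjects). With the same true PAR in all subjects, the mean is too low by f × true PAR.

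| Assumed *r* (true Day 14 PAR) | f = 25% | f = 50% | f = 75% |
|---|---|---|---|
| 5% (9.75) | 2.4 | 4.9 | 7.3 |
| 10% (19.0) | 4.75 | 9.5 | 14.25 |
| 20% (36.0) | 9.0 | 18.0 | 27.0 |

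The range is about 2 to 27 points.

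**Step 4: effect on a comparison**

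If two groups both shrink 10% per week but 75% of one and 25% of the other are not imaged, their Day 14 means differ by 14.25 − 4.75 = 9.5 points with no true difference.

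**The case against.** The strongest reply is that the documents largely settle the point. The Schedule marks area imaging and photos at Visits 4 to 6 without qualification. The text of each of those visits defers to the Schedule for disease assessments, and Protocol Section 5.4 says that keeping to it is essential. The condition can also be read as timing only: measure after debridement, if there is any. The Visit 4 visual examination is worded much the same way, and nobody would call that examination optional. Nor does the absence of footnote 3 mean that imaging may be skipped. The footnote sits in the two columns where debridement is barred; Visit 8 has optional debridement and no footnote, yet its imaging is unconditional.

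Most of this stands. It makes skipping possible rather than expected. It does not remove the conflict: with up to five sites, two readings of one line can yield area data that are complete at some sites and not at others.

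Three stronger readings are tempting and are not supported:

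- A reader might infer that the Day 21 area is exposed too, so that an ulcer shrinking from 4.0 to 2.0 cm² by Day 21 without debridement would read PAR 0%. The Visit 6 parenthesis restricts only the type of debridement. On that text the ulcer is measured and reads (4.0 − 2.0)/4.0 = 50%.
- A reader might infer that sites will skip imaging in some known fraction of visits. The documents give no debridement rate, and the Schedule points the other way.
- A reader might infer that the 28-day endpoint is biased. Visit 7, Visit 8 and early-termination imaging is unconditional.

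**Conclusion.** The point holds as a conflict between the visit text and the Schedule that should be corrected. It is explicit for the area measurement at Visits 4 and 5 and for photos at Visits 4 to 6. It is not established for the Visit 6 area measurement.

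The damage, if a site reads the visit text literally, is confined to descriptive PAR at Days 7 and 14: 0/0 instead of 10/19% for an undebrided ulcer at 10% weekly shrinkage, or roughly 2 to 27 points on a Day 14 group mean. These sizes rest on assumed shrinkage rates (5% to 20% per week), assumed unimaged shares (25% to 75%), and LOCF being applied from baseline. None comes from the documents.

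Day 28 is reached only indirectly, when Visit 7 is missing and the last measured area is an old one because earlier images were not taken. The primary safety endpoint is not affected, and PAR is not one of the efficacy measures for which the SAP plans a test or model. The correction is worthwhile because it costs almost nothing and the lost data could not be rebuilt.

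**What to change.** 1. **Visits 4, 5 and 6 (Protocol Section 8).** Replace the area-imaging and photo lines with: *Measure the target ulcer with the advanced digital imaging system and take digital photos at every visit; if debridement is performed, measure after it and take photos before and after it.*
2. **Footnote 3 (Protocol Section 9).** Reword it rather than extend it to more columns. It now states that no debridement occurs, which would be untrue at Visits 4 to 6, where light debridement is allowed. Suggested text: *At any visit where debridement is not performed, the area measurement and the photographs are still taken.* This general wording also covers the conditional photo lines at Visits 2 and 3.
3. **Optional.** Record on the eCRF whether each area was taken after debridement, so that measurements of the two kinds can be told apart.

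Items 1 and 2 cost a few lines of wording and a short note to sites. Imaging and photos are already scheduled at these visits, so no procedure, visit or subject burden is added. Item 3 costs one data field.
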